6.2 STANDARD CARE AND ADDITIONAL TO STANDARD CARE PROCEDURES

Not applicable.

6.3 RANDOMISATION

Allocation

Sequence Generation

Participants will be randomly assigned to either control or intervention group with a 1:1 allocation as per a computer-generated simple randomisation program such as <https://www.randomizer.org/>.

Implementation

All patients who: 1. fulfil the study inclusion and exclusion criteria 2. give consent for participation in the study, and 3. complete the baseline assessment questionnaire will be randomised to either the intervention or standard-care arm of the study before being provided with a link to access to the MS Online course.

An assigned study investigator will be responsible for allocating participants to either the intervention or standard-care arm.

Participants will be blinded to the nature of the other study arm. That is, there will be no identifying information in the MS Online course and participants will be notified that they are enrolled in a “MS Online Education Course”. Participants will be allocated to the intervention or standard-care arm at a 1:1 ratio using simple randomization.

Research staff (including those researchers performing statistical analyses) will be blinded to the group allocation. Only the researcher responsible for allocating participants to either the intervention or standard-care arm and the data manager will have access to participant allocation information. The same researcher will be responsible for inviting participants to be involved in the qualitative study. In the event this researcher leaves the study, an external researcher will take over this position.

Group allocation information will be concealed from study participants.

6.4 STUDY METHODOLOGY

No clinical or laboratory assessment/s will be carried out as part of this study.

MS-specific program and if so, the program they follow. Eligibility will be assessed by the research team and those participants fulfilling study eligibility will be invited to participate in the study and will be sent a Participant Information Sheet and Consent Form to confirm their consent to participate in the study. Once consent has been confirmed, participants will be sent a link to complete the baseline questionnaire online. Following the collection of baseline data from all recruited participants, randomisation of participants to their respective study arm will be performed. Each participant will then be emailed a link to the MS Online course they have been allocated to (either the MS Online intervention or the MS Online standard-care course) along with general information about the respective MS Online course.

Interested participants assessed as being ineligible for the study will receive an email thanking them for their interest and notifying them of their study ineligibility and explaining why they were ineligible for the study.

Strategies for retention

Retaining participants in the study will maximise the study sample number, the power of statistical analyses, and the likelihood of representativeness. We will undertake multiple strategies to encourage participants to remain in all aspects of the study through consistent follow-up correspondence and social media engagement. All participants will be annually thanked for participating in the RCT.

7.2 INCLUSION CRITERIA

Eligible participants must:

1. Be able to read, write, and speak English;
2. Be 18 years old or over;
3. Have a confirmed diagnosis of relapsing-remitting MS (by a neurologist);
4. Be able to access the internet and be able to view sessions.

7.3 EXCLUSION CRITERIA

Exclusion criteria of participants include:

1. Experiencing any serious co-morbid chronic illness or neurological illness/injury other than MS that would threaten regular participation or significantly affect the outcome measures in

its own right, such as motor neurone disease or stroke, as determined by the study investigators;

2. Currently participating in another study ~~or self-management program involving modification of lifestyle.~~

7.4 CONSENT

Potential participants will be informed of the requirements of participating in the study, which will include:

- Willingness to participate in an MS Online course related to lifestyle modification over a six-week study period;
- Follow-up protocol at baseline, 6 months, 12 months and 2.5 years;
- Potential invitation to be involved in a voluntary qualitative study
- Ability to opt-out at any time.

Consent forms will be provided for review by the Human Research Ethics Committee at the University of Melbourne.

8. PARTICIPANT SAFETY AND WITHDRAWAL

8.1 RISK MANAGEMENT AND SAFETY

There will be no physical distress to participants in the proposed study as the study involves watching an educational course and completing questionnaires online. The exercise component of the MS Online Course in both arms of the study recommends a gentle exercise regimen, if participants decide to implement recommendations, that would not be expected to cause harm.

The research team in conjunction with participants involved in the qualitative interviewing component of the MSOC – Feasibility study found that the MS Online course, questionnaires and qualitative interviewing posed very low psychological distress to participants.

While we do not anticipate potential psychological distress, the following contingency plans will be implemented to address any psychological distress that may arise:

Quantitative research risk management

To address any psychological distress associated with completing online questionnaires at baseline and after 6 and 12 months and 2.5 years after completing the MS Online Course, links will be

provided at the end of questionnaires to country-specific help resources that the participant could access in the event that completing the questionnaires has raised issues for the participant. Participants will also be provided with the contact details of study team members and reminded that they can make contact with a team member if completing the questionnaires has raised any issues for them.

With regards to the HADS survey, while it is a validated tool for assessment of depression, it is not a diagnostic tool. However, we will also provide relevant country-specific resources and/or provide information/links to country-specific help/information at the end of the HADS. Notably, the HADS is the final questionnaire in the survey so this information will be provided directly after answering questions with the greatest potential to cause distress.

Qualitative research risk management

[name] is a specialist emergency physician with 30 years' experience dealing with critically ill and distressed patients. She has skills in managing people in crisis. She has extensive experience dealing with acute and chronic mental health conditions. She is also a member of the Victorian Mental Health Tribunal where she speaks directly with patients with acute mental health disturbance including depression and those at risk of suicide. Although [name] will not provide formal counselling to any participants she has skills to manage difficult emotions and advise appropriate follow up.

[name] is a general practitioner with 5 years of clinical experience. She deals with patients experiencing emotional distress and providing counselling on a daily basis. Although [name] does not intend to provide formal counselling to any participants she has skills to manage difficult emotions and advise appropriate follow up.

[name] conducted qualitative interviews in the MSOC feasibility study but has no formal training in managing people with emotional distress.

At the completion of all qualitative interviews, interviewers will ask participants if the questions or discussions during the interview have raised any distress or psychological difficulties to the participant. In the event any issues have been raised, the interviewer will refer the participant to the relevant country-specific resources and/or provide information/links to country-specific help/information. The interviewer will also notify the participant that they are free to contact them at any later stage if they experience distress after the interview and the same country-specific resources will be supplied to the participant.

Withdrawing participants:

Withdrawing participants will be contacted and provided links to help resources.

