6. STUDY DESIGN

6.1 STUDY TYPE & DESIGN & SCHEDULE

1. Study Type: Clinical trial

Randomised controlled trial, involving:

- a. Epidemiological analysis of quantitative data
- b. Qualitative analysis of semi-structured interviews

2. Study Design (refer to Table 1)

- I. This is a single-site study that will be conducted at the Neuroepidemiology Unit in the Centre for Epidemiology and Biostatistics, Melbourne School of Population and Global Health at The University of Melbourne, involving online recruitment of participants with MS from Australia, New Zealand, USA, UK and Canada. The decision was made to make this a single-site study to guarantee that all data collected from participants (both personal participant data and responses to self-reported questionnaires) will be safely and securely stored in one location (on the University of Melbourne server).
- II. For participant recruitment, details of the RCT will be published on MS society websites and social media sites throughout Australia, New Zealand, USA, UK and Canada seeking interested people with MS to participate in the MSOC - RCT.
- III. Interested participants (people with relapsing-remitting MS) will be asked to click on a link on the notice advertising the MSOC - RCT which will direct them to 7 eligibility questions related to: (1) their age; (2) the type of MS they were diagnosed with; (3) the year they were diagnosed with MS (4,5) whether they follow a MS-specific diet and if so, the diet they follow (6,7) whether they follow a MS-specific program and if so, the program they follow.

- IV. Participants with MS over the age of 18 fulfilling inclusion and exclusion criteria from Australia, New Zealand, USA, UK, Canada and other countries who read, write and speak English will be invited to participate in the study. Note, the recruitment period will be up to two months from the date of the first participant recruitment or earlier, if the required number of eligible participants have been recruited.

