The complete patient-reported questionnaire with approximately 150 questions has been found to take approximately 60 minutes to complete. Participants will be able to login and complete this questionnaire over time. The participants will be requested to complete this questionnaire on four separate occasions (baseline, 6 months, 12 months and 2.5 years) and due to previous studies that we have performed within the Neuroepidemiology Unit utilising questionnaires of a similar length over 7.5 years ((Marck et al., 2018; Weiland et al., 2018), we do not believe the questionnaire will create an unacceptable burden on participants.

Quantitative data analysis:

We will measure adherence to lifestyle modification recommendations in people with MS enrolled in the MS Online intervention and the MS Online standard-care arm (control) using validated patient-reported questionnaires.

We will examine and compare clinical and health outcomes of depression, anxiety, fatigue, disability, self-efficacy and quality of life in people with MS in the short-term (6 months and 12 months) and medium-term (2.5 years) in people enrolled in the MS Online Intervention course arm and people enrolled in the MS Online standard-care course arm.

Statistical analyses will enable us to examine whether a causal relationship exists between lifestyle factors and clinical and health outcomes in people with MS. These analyses are anticipated to be completed within 6-12 months of collecting data for short-term and long-term analyses, respectively.

Qualitative data:

Qualitative data will comprise edited transcripts of recordings from semi-structured interviews from 15 randomly selected participants from the intervention arm and the standard-care arm carried out within one month of completing the MS Online course and 12 months after completing the MS Online course (the same people will be interviewed at both time points).

Interviews will be digitally recorded and transcribed by voice recognition software. Data will be stored in a re-identifiable format and encrypted files will be securely stored as described in Section 10.

Qualitative data collection feasibility:

The qualitative component of the MSOC – RCT is similar to the qualitative component of the MSOC – Feasibility study we performed. This interviewing technique was found to be both effective and participants reported positive feedback following interviews.

Qualitative data analysis:

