8.2 HANDLING OF WITHDRAWALS

Participants will be notified that they can withdraw from the study at any time for any reason. If a participant wishes to withdraw from the study, we would advise them to contact us so as to avoid receiving unwanted study emails and phone calls related to follow-up in the future.

We do not anticipate any adverse events for the participant if they wish to withdraw from the study, however, we will provide withdrawing participants links to help resources. The participant will also be notified that all of their data will be retained and stored in a confidential and secure manner (Section 10).

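### Section 8.1 places the distress help links only at the end of an hour-long survey that can be done in several sittings, and provides none for a participant who stops part-way without withdrawing

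*Combined protocol and SAP*

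**What the plan says.** Under quantitative risk management, section 8.1 says links will be "provided at the end of questionnaires to country-specific help resources that the participant could access" if the questions have raised issues. It adds, for the HADS, "links to country-specific help/information at the end of the HADS". The reason given for the position, with distress in mind, is: "Notably, the HADS is the final questionnaire in the survey so this information will be provided directly after answering questions with the greatest potential". The same section promises team contact details and a reminder that participants may use them, but does not say when or where these appear.

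On the survey itself, section 6.1 states: "The complete patient-reported questionnaire with approximately 150 questions has been found to take approximately 60 minutes to complete". It continues: "Participants will be able to login and complete this questionnaire over time". The survey is given at baseline, 6 months, 12 months and 2.5 years.

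On people who leave, section 8.1 says the team will contact withdrawing participants and give them links to help resources. Section 8.2 repeats the promise of links and tells a participant who wants to withdraw: "we would advise them to contact us so as to avoid receiving unwanted study emails and phone calls". Section 8.3 describes withdrawal more broadly, as not completing the course and all of the follow-up questionnaires.

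**The concern.** Psychological distress is the only participant risk for which the protocol makes contingency plans. Placing the links after the HADS serves the person who finishes: help appears straight after the items judged most likely to upset. It does not serve the person who stops before that page.

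Stopping part-way is allowed by design. Section 12 records that the focus group accepted the length provided the survey could be spread over time. A participant who keeps to the plan may therefore close one or more sittings before reaching any link. Many items that could trouble someone come earlier, including the MSQOL-54, the disability scale and the fatigue scale. If distress is the reason for stopping, the stated position misses that person at the moment when the links would be useful.

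The stake is participant care. No effect on the estimates or error rates is claimed.

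**Working it through.** No sample-size or error-rate formula applies. The check has two parts: how much of the survey precedes the links, and who could stop without seeing them.

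**Share of items before the HADS**

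Inputs:
- Item counts per instrument and totals per occasion, from Table 1 in section 6.1.
- HADS length of 14 items, from Table 1.
- HADS in last position, from section 8.1. Table 1 lists it before the fatigue and self-efficacy scales, but table order need not be survey order.

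Reproducing the plan's totals first:
- Baseline: the items sum to 166; Table 1 states 166.
- 6 months: 166 less the 7 items asked at baseline but not at 6 months (consent 1, age 1, sex and gender 2, address 1, country of birth 1, education 1) = 159; stated 159.
- 2.5 years: 159 + 1 (address) = 160; stated 160.
- 12 months: the items sum to 159, but Table 1 states 166. The stated total arises only if the 7 qualitative items are added (159 + 7), although the row is labelled as leaving them out. This does not affect the point.

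Share before the HADS = (total − 14) / total:
- Baseline: 152/166 = 92%
- 6 months: 145/159 = 91%
- 2.5 years: 146/160 = 91%
- 12 months: 91% with 159 items, 92% with 166
- With the rounded figure of 150 questions in section 6.1: 136/150 = 91%

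If every item takes equal time (an assumption), the HADS begins at about 60 × 152/166 = 55 minutes. The links come after its 14 items.

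**Who could stop without seeing the links**

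- *A randomised participant at a follow-up survey.* Section 6.3 randomises only those who have completed the baseline questionnaire, so this person should have reached the links at least once. Stopping part-way at 6 months, 12 months or 2.5 years means not being shown them in that sitting.
- *A participant who stops during the baseline survey.* Under section 6.1 this person has already consented, but under section 6.3 is not randomised. If they do not return, they may never see the links.
- *A participant who formally withdraws.* Sections 8.1 and 8.2 provide links.
- *A participant who simply stops.* Section 8.2 advises those wishing to withdraw to make contact, which this person has not done. The wider description in section 8.3 might bring them under the promise in section 8.1, but no section gives a trigger or a time for contacting them. It does not plainly reach someone who stops at baseline, before any course has been allocated.

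No section puts links on the first page, on each page, on an exit screen or in emails. Section 6.1 mentions reminders to complete questionnaires, but not as a safety measure.

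**The case against.** The strongest case is that the safeguard is wider than its position in the survey suggests.

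- *Randomised participants have already seen the links.* This stands. A reader might infer that people who stop never reach the protection, but for anyone randomised that is not supported. One viewing at baseline is still weaker than having the links at hand up to 2.5 years later.
- *Team contact details are provided.* This also stands, and they are not tied to the end of the survey. Their timing and place are unstated, so they narrow the gap without clearly closing it.
- *The withdrawal route may cover non-completers.* Sections 8.1 and 8.3 read together allow this, and the advice in section 8.2 to contact the team is not a condition for receiving links. It cannot be said that the route misses these people, only that the three sections leave it unsettled.
- *The plural in section 8.1 could mean the end of each instrument.* This is possible, because the section calls the HADS a questionnaire within the survey. On that reading the 91% to 92% loses its force. The separate HADS sentence, and the emphasis on the HADS being last, make the end of the survey the more natural reading.
- *The survey and information form are attachments that cannot be seen here.* True. They may already carry the links.
- *Distress is expected to be very low.* Section 8.1 reports this from the feasibility interviews, and section 12 from a focus group of 5. It bears on how often help is needed, but says little about people who stop.

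A reader might also infer that the links fail participants recruited "from Australia, New Zealand, USA, UK, Canada and other countries". The documents do not support that: the resources are described as country-specific without being limited to the five named countries, and country is collected at baseline.

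**Conclusion.** The point holds in a limited form. The only stated position for the links within the survey is its end, after 91% to 92% of the items and then the HADS itself. A participant who stops part-way without withdrawing is not shown them in that sitting. Someone who stops during the baseline survey and does not return may never see them.

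This rests on the natural reading of section 8.1 and on the HADS being last, as that section says.

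No number of people can be attached. A reader might take a share of the expected 42% loss by 12 months (0.42 × 1054 = about 443) as people left without the safeguard. That does not follow. All 1054 should have passed the links at baseline, those who stop during baseline are outside the 1054, the loss includes people who may never open a survey, section 9.1 calls the figure a likely overestimate, and the share who stop mid-survey is not given.

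The gap is small and affects participant care, not validity. It is worth closing because the remedy costs almost nothing.

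**What to change.** In section 8.1:

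1. Keep the links after the HADS.
2. Show the same links and the team contact on the survey's first page, as a footer on every page or on the save-and-exit screen, and in the existing invitation and reminder emails, identically in both arms.
3. State that the links promised to withdrawing participants also go to anyone who leaves a survey unfinished, including the baseline survey, and reconcile sections 8.1, 8.2 and 8.3 on who counts as withdrawing.

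If the attached survey or information form already does this, a sentence in section 8.1 saying so is enough for item 2.

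The cost is minor edits to the survey template and email text. No items or visits are added, and because the content is the same in both arms it creates no difference between them.

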8.2 HANDLING OF WITHDRAWALS

Participants will be notified that they can withdraw from the study at any time for any reason. If a participant wishes to withdraw from the study, we would advise them to contact us so as to avoid receiving unwanted study emails and phone calls related to follow-up in the future.

We do not anticipate any adverse events for the participant if they wish to withdraw from the study, however, we will provide withdrawing participants links to help resources. The participant will also be notified that all of their data will be retained and stored in a confidential and secure manner (Section 10).

8.3 REPLACEMENTS

Participants that withdraw from the study will not be replaced. (That is, participants that do not complete the MS Online course and all related follow-up in the form of completing MS Online questionnaires). The calculation of the sample size (Section 8.1) allows for a proportion of participants not complete to all components of the MS – RCT study (42% loss to follow-up) and still retain sufficient statistical power.

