- V. Interested participants meeting the study eligibility criteria (Refer to Section 6.2 and 6.3 for eligibility criteria) after completing the eligibility questions will be emailed a participant information form and consent form. Once participants have provided their consent by ticking a box online, participants will be emailed a link to the baseline questionnaire to obtain demographic data and obtain data on lifestyle and outcome measures (Section 4.3, Table 1). Interested participants not meeting the study eligibility criteria will be excluded and notified by email that they were not eligible to participate in the study and thanking them for their interest.
- VI. Participants will be randomised to either the MS Online intervention course or the MS Online standard-care course at a ratio of 1:1 using simple randomisation. Randomisation will occur over a 2-week period after recruitment of eligible participants.
- VII. Participants will undertake the MS Online course (intervention arm or standard-care arm) over a 6-week period. Note, each arm is of comparable length and content-type (video, interviews, images, interactivity), to minimise variability in 'dose' received between intervention and standard-care groups. Both courses will follow a similar structure throughout, limiting differences in how the content of the course is presented.
- VIII. Patient-reported outcomes measures (Section 4.3, Table 1) will be determined after a period of 6 months, 12 months and 2.5 years after the completion of the MS Online course. This will involve participants from the MS Online intervention arm and the MS Online standard-care arm completing validated questionnaires online (following instructions and reminders, if necessary, from study team members). These measures will determine participants adherence to lifestyle recommendations of the Online intervention and standard course with respect to diet, exercise, omega 3 intake, vitamin D intake, meditation and sun exposure (Table 1). Health outcomes related to participant's quality of life, depression, anxiety, fatigue, disability and self-efficacy.
- IX. The primary objective of the study will be assessed at the 12-month and 2.5 year follow-up. That is, Health-related quality of life (HRQOL) calculations for Physical Health Composite

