9. STATISTICAL METHODS

9.1 SAMPLE SIZE ESTIMATION & JUSTIFICATION

The two primary outcome measures for this study are changes in Physical Health Composite (PHC) and Mental Health Composite (MHC) derived from the MSQOL-54. PHC and MHC are derived by combining scores of relevant subscales (Vickrey et al., 1995). For the proposed MSOC – RCT, sample sizes were calculated in order to detect a 5-point difference in the PHC and MHC scores (a minimum clinically meaningful change in these HRQOL measures, between the intervention and standard-care arms).

To further account for loss-to-follow-up from the study period, based upon MSOC - Feasibility results, we anticipated a 42% loss-to-follow-up between randomisation and follow-up at 12 months. It is likely

this level of loss-to-follow-up is an overestimate of what will be observed in the proposed MSOC – RCT due to redevelopment of the intervention based upon feasibility data, but this overestimate will account for participants in the standard-care course that request access to the MS Online Intervention course after unblinding at 12 months after participants undertake the MS Online Standard-care course.

Taking these factors into account, we estimate 1054 participants, 527 in each arm (1:1 allocation) with data at baseline and follow-up would give 80% power to detect a 5-point change in HRQOL across both PHC and MHC outcomes. This estimation of power is based on the mean PHC and MHC scores and their SD, which is the SD between groups at baseline.

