9.2 POWER CALCULATIONS

Power calculations were estimated using the Bonferroni correction. The Bonferroni correction adjusts probability (p) values because of the increased risk of a type I error when making multiple statistical tests (in this instance, the increased risk of type I error for the multiple outcomes of PHC and MHC scores of HRQOL, as assessed by the MSQOL-54 questionnaire) (Osoba et al., 1998; Taphoorn, et al., 2005).

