9.3 STATISTICAL METHODS TO BE UNDERTAKEN

Quantitative data analysis:

Clinically significant fatigue will be defined as a mean FSS > 5 (Krupp et al., 1989). Anxiety and depression will be defined as higher HADS (Zigmond & Snaith, 1983). The UWSE will be assessed as a continuous term and dichotomised at the median as there is no established cut off point indicating sufficient self-efficacy.

Characteristics of quality of life (QoL) will be measured by the MSQOL-54, including physical and mental health composite scores and multiple subdomains. Linear regression will be used to determine cross-sectional and prospective relationships with QoL. Characteristics of disability will be assessed using linear regression. Characteristics of dichotomous clinically significant fatigue, depression and anxiety will be assessed by log-binomial regression. Characteristics of Self-efficacy composite scores will be assessed by linear and log-binomial regression for continuous and dichotomised self-efficacy, respectively. Characteristics of perceived social support scores will be

assessed by linear regression. All models will be assessed for potential confounders and appropriate adjustments will be made in analyses.

Qualitative data analysis:

Audio recordings will be transcribed for analysis and stored within Nvivo Software (www.qsrinternational.com) to enable data management. Data analysis will be conducted within a qualitative paradigm using reflexive thematic analysis (Braun 2014). Reflexive thematic analysis is considered the most appropriate analytic process due its lack of grounding in a particular philosophy (Braun 2006), and as a method suitable to exploring people's experiences, views and perceptions (Braun 2014) and its allowing expression of results in a way accessible to those in the wider community. Reflexive thematic analysis also emphasises the importance of the researcher being deeply involved in the research. Data will be analysed by the process of data familiarisation, coding, and theme development and refining. Data extracts (quotes) will illustrate themes.

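### The expected 42% loss by 12 months is met only with a larger sample; the linear regression named for quality of life has no missing-data method and by default omits everyone lost by then

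*Combined protocol and SAP*

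**What the plan says.** Section 9.1 states that "we anticipated a 42% loss-to-follow-up between randomisation and follow-up at 12 months", based on the feasibility study. Section 8.3 says that withdrawals are not replaced and that the sample size allows for "42% loss to follow-up) and still retain sufficient statistical power". Those two sections are all the plan says about dealing with the loss. Section 7.1 gives representativeness as one reason for retention efforts, but not as a matter for the analysis.

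The method is in Section 9.3: "Linear regression will be used to determine cross-sectional and prospective relationships with QoL", with adjustment for confounders that are not named. Nowhere does the document give an analysis set, an intention-to-treat statement, a repeated-measures model, imputation, weighting or a missing-data sensitivity analysis.

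The data for a better analysis will exist. Under Section 6.1 (item VIII), outcomes "will be determined after a period of 6 months, 12 months and 2.5 years after the completion of the MS Online course", and Table 1 lists the MSQOL-54 at baseline and at all three follow-ups. Item IX places the assessment of the primary objective at 12 months and 2.5 years. Section 8.2 keeps the data of people who withdraw. The Data Analysis text that closes Section 12 lists a statistical analysis plan as still to be developed.

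**The concern.** A regression of the 12-month score on arm and baseline covariates uses only people observed at 12 months, unless something else is specified. A participant who answers at baseline and 6 months and is then lost contributes nothing to the 12-month or 2.5-year comparison, although the 6-month score is a strong predictor of the missing value. That score does still serve the 6-month comparison.

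Enlarging the sample protects power. It does not protect against bias, because the bias does not shrink as the number randomised grows. With about two-fifths of the 12-month outcomes expected to be missing, the way they are handled could move the primary estimate. Leaving that choice until the data have been seen would weaken the result.

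**Working it through.** **1. The plan's sample size.** The inputs from Sections 9.1 and 9.2 are a 5-point difference, 80% power, a Bonferroni correction over two outcomes, 42% loss and 527 per arm. Section 9.1 gives no SD, and neither overall alpha nor sidedness is stated. I assume two-sided 0.05 overall, so 0.025 per outcome, and SD 20.

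n per arm = 2 × SD² × (z for 1 − α/2 + z for power)² / difference² = 2 × 400 × (2.241 + 0.842)² / 25 ≈ 304.2, or 305 after rounding up.

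Allowing for loss: 305 / 0.58 = 526 per arm, 1052 in total, against the stated 527 and 1054. The stated size therefore fits an SD of about 20. With 305 per arm, power is 88% at SD 18, 80% at SD 20 and 71% at SD 22.

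**2. Who is missing at 12 months.** Observed: 527 × 0.58 ≈ 306 per arm. Missing: 527 − 306 = 221 per arm. The documents do not split this loss into before and after 6 months, so two splits are shown:

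- 20% lost before 6 months: 527 × 0.20 ≈ 105 per arm have no 6-month score, and 221 − 105 = 116 have one. Loss after 6 months is 1 − 0.58/0.80 = 27.5% of those still present.
- 35% lost before 6 months: 527 × 0.35 ≈ 184 have no 6-month score, and 221 − 184 = 37 have one. Loss after 6 months is 1 − 0.58/0.65 = 10.8%.

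**3. Bias of the completer regression.** Assumptions: normal scores at baseline, 6 and 12 months, SD 20, correlations 0.6 to 0.7, and total loss 42%. The log-odds of loss after 6 months fall by 0.02 or 0.04 per point of 6-month improvement. With 20% early loss and a change SD of 20 × √(2 × (1 − 0.6)) = 17.9, those slopes mean loss after 6 months of 35% against 21%, or 44% against 16%, at one SD below and above the mean change. The analysis is linear regression on arm and baseline in those observed at 12 months.

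| Dependence on 6-month change | Lost before 6 months | Estimate, true 5 | Estimate, true 0 |
|---|---|---|---|
| Intervention arm only | 20% | 5.6 to 6.2 | 0.7 to 1.3 |
| Intervention arm only | 35% | 5.3 to 5.5 | 0.3 to 0.6 |
| Intervention arm only | 38% | 5.1 to 5.3 | 0.1 to 0.3 |
| Same in both arms | 20% | 4.9 | 0.0 |

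For 20% to 35% early loss with intervention-arm-only dependence, the bias is 0.3 to 1.3 points, or 6% to 26% of the 5-point target. For scale, the standard error of the 12-month contrast is about 20 × √(2/306) = 1.6 unadjusted, or 1.6 × √(1 − 0.6²) ≈ 1.3 after baseline adjustment.

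**4. Outer cases.** Suppose all loss comes after the 6-month answer, at correlation 0.6, with the log-odds changing by 0.25 to 2 per SD of change:

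- Intervention-arm-only dependence gives 5.5 to 7.6 for a true 5 and 0.5 to 2.8 for a true 0.
- The same dependence in both arms gives 4.96 down to 4.46 for a true 5 and about 0 for a true 0.

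In these runs loss was between 38% and 46% in each arm, so similar dropout rates would not rule the bias out.

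**5. Using the 6-month score.** In the step 4 cases, a likelihood-type analysis that includes it returned 4.95 to 5.01 for a true 5 and −0.04 to 0.03 for a true 0. This is expected by construction, because loss was generated from the observed 6-month score. Where the mechanism is not arm-specific, the gain in standard error is only 2% to 4%.

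**The case against.** The strongest reply is that nothing in the documents shows loss depending on results differently by arm. Section 6.3 keeps participants blind to the nature of the other arm, and Section 6.1 matches the courses in length, content type and structure. This stands. The mechanism is a plausible risk in an unsupervised online course, not a documented fact.

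Second, the 42% comes from a feasibility study run from April to June 2021 (Sections 4.1 and 4.3), and Section 8.3 describes withdrawal as including failure to finish the course. This suggests, without proving, that much of the loss is early. The bias is then at the low end, and a repeated-measures model has only the baseline score to use for those people. This also stands.

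Third, the plan does not say that only completers will be analysed, and a statistical analysis plan is still to come. The omission is inferred from the default behaviour of the named method. The inference is fair because nothing in the text overrides it, and the plan still to be written is a place for the fix, not evidence that the gap is filled.

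A reader might infer more: that the regression is biased whenever loss depends on the 6-month result, or that the primary estimate will overstate the effect. Neither follows. The same dependence in both arms gives no bias under no effect and only a slight attenuation otherwise. The direction also depends on the mechanism: with no true effect, putting the same dependence in the standard-care arm instead reverses the sign.

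**Conclusion.** The concern holds as a conditional one. The plan expects 42% loss by 12 months, meets it only through the sample size, and names a method that by default sets aside the earlier scores of the people lost. If loss after 6 months depends on the 6-month result differently by arm, the completer estimate is biased. The size is about 0.3 to 1.3 points under SD 20, correlations 0.6 to 0.7, dependence on poor change in the intervention arm only, and 20% to 35% lost before 6 months. It shrinks further as more of the loss falls early.

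The SD, the correlations, the timing and the mechanism are all assumptions; the documents give none of them. No loss rate is given for 2.5 years, so no size is put on that comparison. The documents do not support saying that the trial's estimate is or will be inflated. They do support changing the named analysis before the 12-month data are examined, since the change is cheap and the expected loss is large.

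**What to change.** In Section 9.3, or in the analysis plan still to be developed, make the primary analysis of PHC and of MHC a likelihood-based mixed model for repeated measures. Include all randomised participants by assigned arm, use baseline, 6, 12 and 30 months, fit arm-by-time terms with an unstructured covariance, and handle baseline within the model. Take the 12-month and 2.5-year contrasts from it.

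This model corrects only for loss that depends on observed scores, and it recovers little for people lost before 6 months. Add one sensitivity analysis that imputes the missing scores, shifts them by a stated range separately in each arm, and reports the shift at which the conclusion changes (a tipping point).

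The cost is some wording and modest extra programming. No new data, visits or participants are needed.
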